6.4 Accountability Procedures

Subjects will be provided with a drug diary at each time point when drug for inhalation is dispensed (baseline, week 7, and week 15 for the core study, and week 23, week 30, and week 38 for the extension phase). Subjects will be instructed to return all drug for inhalation consumed and remaining, as well as a completed diary, at weeks 7, 15, 23, 30, 37, and 47. Reconciliation of drug consumed and drug remaining will be logged on the drug dispensing and return log, signed and dated. Any discrepancies noted will be investigated, resolved, and documented prior to return or destruction of unused study drug. Drug destroyed on site will be documented in the study files.

6.5 Assessment of Subject Compliance

Subjects will be instructed to return empty study medication containers at weeks 7, 15, 23, 30, 37, and 47. Site personnel will review returned study medication to determine compliance.

6.6 Prior and Concomitant Therapy

Throughout the study, the subject may be prescribed concomitant medications or treatments deemed necessary to provide adequate supportive care provided that the medications are licensed in the United States. All concomitant medications and/or treatments received by a subject should be recorded on the appropriate source document and eCRF.

6.6.1 Prohibited Medications and Contraindications

Prohibited Medications

Prohibited medications for subjects in the Imaging group are as follows:

- 1- immunomodulatory medications
- 2- nicotine replacement products such as gum or patch

Additionally, subjects in the Biomarker group should wash from benzodiazepines and non-steroidal anti-inflammatory medications one week prior to PET scan as these compounds would affect the results of the scan.

Pregnancy & Nursing Mothers

There are no adequate and well-controlled studies in pregnant women. Subjects or partners of male subjects should not become pregnant during the study or 3 months after stopping study drug. If a female subject becomes pregnant, study treatment must be discontinued immediately.

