3 OBJECTIVES

3.1 Study Objectives

The primary objectives of the study are to determine the safety and tolerability of RNS60 in 18 patients with ALS. The following clinical outcomes will be collected: ALS functional rating scale (ALSFRS-R), slow vital capacity (SVC), strength (measured by ATLIS- Accurate Test of Limb Isometric Strength). An additional primary objective is to measure the impact of RNS60 on several markers of neuro-inflammation measured by blood biomarkers in all subjects and by [¹¹C]-PBR28 positron emission tomography (PET) imaging in a subgroup of 13 subjects.

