3.2 Study Outcome Measures

For all subjects enrolled in the study, the following will be primary outcome measures:

- 1- Safety, as measured by AEs and clinically meaningful changes in vital signs, physical examination, and standard clinical laboratory tests;
- 2- Tolerability, defined as the ability of subjects to complete the entire 24-week treatment portion of study;
- 3- Clinical outcomes: Measured by ALSFRS-R, SVC, and strength (measured by ATLIS).
- 4- Blood biomarkers of inflammation.

For subjects in the “Imaging group”, the following additional outcome measures will be obtained:

- 1- Neuroimaging biomarkers ([¹¹C]-PBR28-PET) including both regions of interest (ROI) and voxel-based analyses

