5.2.2 Subject Exclusion Criteria

Study subjects meeting any of the following criteria during screening evaluations will be excluded from entry into the study:

- 1- Abnormal liver function defined as AST and/or ALT > 3 times the upper limit of the normal.
- 2- Renal insufficiency as defined by a serum creatinine > 1.5 times the upper limit of normal.
- 3- The presence of unstable psychiatric disease, cognitive impairment, or dementia that would impair ability of the participant to provide informed consent, according to PI judgment.
- 4- Clinically significant unstable medical condition (other than ALS) that would pose a risk to the participant if they were to participate in the study.
- 5- History of HIV, clinically significant chronic hepatitis, or other active infection.
- 6- Active participation in another ALS clinical trial within 30 days of the Screening Visit

Study subjects in the Imaging group meeting any of the additional following criteria during screening evaluations will be excluded from entry into the study:

- 1- Exposure to immunomodulatory medications within 30 days of the Screening Visit.
- 2- Any contraindication to undergo MRI studies such as
 - a. History of a cardiac pacemaker or pacemaker wires
 - b. Metallic particles in the body
 - c. Vascular clips in the head
 - d. Prosthetic heart valves
 - e. Claustrophobia
- 3- Radiation exposure that exceeds the site's current guidelines

- 4- Current use of tobacco products including cigarettes, cigars, snuff and chewing tobacco, or nicotine replacement products such as gum or patch.
- 5- Current use of medications / treatments under investigation in ALS clinical trials or use of “off-label” medications for ALS as determined by the clinical judgment of the principal investigator.

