5.3 Withdrawal

A study subject will be discontinued from participation in the study if:

- Any clinical AE, laboratory abnormality, concurrent illness, or other medical condition or situation occurs such that continued participation in the study would not be in the best interest of the subject.
- The participant meets any exclusion criteria (either newly developed or not previously recognized).

Subjects are free to withdraw from participation in the study at any time upon request.

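### Immunomodulators are barred only in the Imaging group, although blood inflammation markers are a primary outcome in every subject of this single-arm trial

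*Combined protocol and SAP*

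**What the plan says.** **Outcome.** Section 3.1 names as an additional primary objective the effect of RNS60 on "several markers of neuro-inflammation measured by blood biomarkers in all subjects". Section 3.2 lists "Blood biomarkers of inflammation" among the primary outcome measures for all enrolled subjects. Blood for these markers is drawn at Baseline, Week 11 and Week 23 (core Schedule of Activities; 7.2, 7.4, 7.5).

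**Entry.** Section 5.2.2 has one list for everyone and a second that begins "Study subjects in the Imaging group meeting any of the additional following criteria during screening evaluations will be excluded from entry into the study". Two items on the second list matter here: item 1, "Exposure to immunomodulatory medications within 30 days of the Screening Visit", and item 5, "Current use of medications / treatments under investigation in ALS clinical trials or use of “off-label” medications for ALS".

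**On study.** The list in 6.6.1, headed "Prohibited medications for subjects in the Imaging group are as follows", names immunomodulators and nicotine replacement. For all subjects, 6.6 says that "the subject may be prescribed concomitant medications or treatments deemed necessary to provide adequate supportive care", on condition of a US licence, and requires all such treatment to be recorded. Section 5.3 discontinues a subject if "The participant meets any exclusion criteria (either newly developed or not previously recognized".

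**NSAIDs.** Section 6.6.1 asks for a one-week washout of NSAIDs and benzodiazepines before the PET scan, because these drugs would affect the scan. It says nothing about the blood draws.

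**Analysis.** The statistical section, 6.7, covers adverse events, tolerability and PET. The visible text gives no analysis of the blood markers and no rule for using the medication log in one.

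**The concern.** The trial is open label with one arm, so any effect on a blood marker is read from change within subjects. An immunomodulator started or stopped between draws acts on the quantity being measured, and no concurrent group shows what would have happened without RNS60. The protocol accepts this reasoning for PET, where it restricts such drugs and explains the washout by their effect on the scan. It gives no reason for leaving the other primary inflammation readout without the same protection in subjects who are not imaged. At stake is how far a change in the all-subject blood markers can be interpreted. Safety and tolerability assessment is not affected.

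**Working it through.** **1. The plan's own figures.** Those checked in 6.7 reproduce. The chance of at least one event with a true rate of 15% in 15 subjects is 1 − 0.85^15 = 0.913 (stated: over 90%). The chance of 10 or more of 15 tolerating the drug is 0.852 at a true rate of 75% and 0.034 at 40% (stated: 85% and 3%). None of these concerns the blood markers, so there is no stated biomarker figure to check.

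**2. Subjects outside both immunomodulator rules.** Formula: (treated − imaged) / treated.

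| Treated | Imaged | Source | Outside the rules |
|---|---|---|---|
| 18 | 13 | Section 3.1 | 5/18 = 28% |
| 18 | 10 | Protocol Summary, Study Population (10) | 8/18 = 44% |
| 15 | 10 | Section 6.7 | 5/15 = 33% |

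**3. Shift in the mean change.** The documents give no effect of an immunomodulator on these markers, so the size is assumed. Let m subjects of 18 each have their change moved by k SDs of the change score, all in one direction. The mean moves by m·k/18 SD.

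- One subject: k = 1 gives 1/18 = 0.06 SD; k = 2 gives 0.11 SD; k = 3 gives 0.17 SD.
- Two subjects: k = 1 gives 0.11 SD; k = 2 gives 0.22 SD; k = 3 gives 0.33 SD.

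**4. In standard errors.** With the SD unchanged, the shift is m·k/√18 standard errors. Shifted subjects also widen the sample SD: the expected variance becomes 1 + k²·m(18 − m)/(18·17).

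| m | k | SD unchanged | SD widened |
|---|---|---|---|
| 1 | 2 | 0.47 | 0.47/√1.222 = 0.43 |
| 1 | 3 | 0.71 | 0.71/√1.500 = 0.58 |
| 2 | 2 | 0.94 | 0.94/√1.418 = 0.79 |
| 2 | 3 | 1.41 | 1.41/√1.941 = 1.02 |

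The widened figures are the fair ones.

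**5. Effect on a test, as an illustration.** The plan specifies no test for these markers. A two-sided 5% one-sample t test was simulated with no RNS60 effect. With one subject of 18 shifted by 1 SD, it rejects about 5% of the time. If every uncovered subject shifted by 1 SD in the same direction, it would reject about 15% (5 subjects) or 34% (8 subjects). That is an extreme case, not an expectation.

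**6. NSAID timing.** The first scan may fall on the Baseline day (7.2), so the baseline sample can be drawn off NSAIDs. No scan falls near Week 11. The second scan may fall anywhere from Week 18 to Week 23 (7.3, 8.1.12), so up to 23 − 18 = 5 weeks before the last draw. Even an imaged subject can therefore contribute an off-to-on contrast in NSAID use.

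**The case against.** The strongest reply is that this is a small pilot sized on safety and tolerability, that lighter restrictions outside imaging help recruitment, and that extending them would still not make a marker change attributable to RNS60. All of that is true. It limits what the remedy achieves, but does not explain why one primary inflammation readout is protected and the other is not.

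Several stronger readings are tempting, and the documents do not support them.

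- **Non-imaged subjects face no drug restriction.** They do face some: no active participation in another ALS trial within 30 days of Screening, riluzole absent or stable for 30 days before it, and supportive-care drugs with a US licence only. None of these addresses immunomodulators as such.
- **The exclusion of off-label and investigational ALS drugs lapses after entry.** It is worded as current use, and 5.3 discontinues anyone who newly meets an exclusion criterion, so for imaged subjects it carries into treatment.
- **That exclusion should therefore be extended to everyone.** Through 5.3, this would force discontinuations, which count against tolerability as defined in 3.2 and 6.7.
- **Samples drawn after a drug change should be dropped from the main result.** A drug may be started because of inflammation or an adverse event, so dropping those samples selects on a post-baseline event.

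It is also fair that a drug taken stably throughout need not produce a change, that concomitant medication is already reviewed at every draw visit, and that the NSAID scenario needs particular scan dates and resumed use.

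**Conclusion.** The point holds as a cheap improvement to a stated primary outcome. The immunomodulator rules cover a narrower group than the blood biomarker outcome, leaving 5 or 8 of 18 subjects outside them. The exposure comes from those among them who stop just before entry, or start or stop between draws, not from all 18 subjects.

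The size of the bias is unknown. On an assumed shift of 1 to 3 SD, one such subject moves the mean change by 0.06 to 0.17 SD. At the low end this is negligible; with two subjects at 3 SD it reaches about one standard error. These figures assume shifts in one direction, and the documents say nothing on how many subjects would change drugs.

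A reader might infer that ALSFRS-R, SVC and strength are biased to a similar degree. They too are listed as primary for all subjects in 3.2, but nothing in the documents allows an effect on them to be sized, so the conclusion is confined to the blood markers.

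**What to change.** 1. Move Imaging-group exclusion 1 in 5.2.2 (immunomodulator exposure within 30 days of Screening) to the list for all subjects. It is anchored to Screening, so starting such a drug on study would not newly meet it and would not trigger discontinuation under 5.3.
2. Keep all samples in the main biomarker summary. Beside it, prespecify a supportive analysis that leaves out samples drawn after an immunomodulator, or an off-label or investigational ALS drug, was started or stopped since Baseline. Use the concomitant medication log already kept, and flag NSAID use in the 7 days before each draw.
3. Have the sponsor reconcile 6.6, 6.6.1 and the withdrawal rule in 5.3 with the all-subject biomarker outcome. Which on-study medication or discontinuation rule should apply is for the sponsor to decide. In the same pass, settle whether 13 or 10 subjects are imaged, whether 18 or 15 are treated, and whether the Biomarker group in 6.6.1 and 6.7 is the Imaging group.

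The cost is a slightly narrower pool for the non-imaging places, some protocol wording and one extra analysis. Because that analysis selects on a post-baseline event, it can only be supportive.

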6.7 Statistical considerations

Sample size calculation was based on the primary outcomes of safety and tolerability. With a sample size of 15 participants, we will have over a 90% chance of seeing at least one occurrence of any adverse event whose probability of occurrence is 15% or greater. Tolerability will be defined as the ability of subjects to complete the entire 24-week treatment portion of study. With 15 participants on active drug in this study, if 10 or more participants tolerate the drug, there is an 85% chance that the true tolerability among people with ALS is at least 75%. Furthermore, if 10 or more people tolerate the drug, there is only a 3% chance that the true tolerability will be as low as 40% in people with ALS. For people in the Biomarker group, primary outcomes will include changes in the ROI in the motor cortex as assessed by [11C]-PBR29-PET. Our previous studies comparing mean PBR28 binding in the motor cortices in limb-onset ALS subjects (1.18 units) with matching healthy volunteers (1.064 units) revealed 0.116 mean difference between the two groups, with 0.08 standard deviation in the ALS group. With 10 people in the Biomarker group, the probability is 90 percent that the study will detect a treatment difference at a one-sided 0.1 significance level if the true difference is 0.096 units.

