The primary objectives of the study are to determine the preliminary safety and tolerability of RNS60 treatment in 18 people with ALS over 24 weeks. We will measure the impact of RNS60 on blood biomarkers of inflammation. In addition, in a subgroup of 13 study participants (“Imaging group”), an additional primary objective is to measure the impact of RNS60 on [¹¹C]-PBR28 uptake in the motor cortices and brain stem measured by positron emission tomography (PET) imaging.

RNS60 in ALS

V6.0

5/5/2016

We will also measure the effect of RNS60 on ALS clinical outcomes [ALS functional rating scale (ALSFRS-R), slow vital capacity (SVC), strength (measured by ATLIS- Accurate Test of Limb Isometric Strength)].

For participants who elect to continue with the optional 24 week extension, safety parameters (labs, EKG, adverse events, C-SSRS) will continue to be monitored. We will also collect ALSFRS-R and SVC outcome measures.

Study Location

Massachusetts General Hospital (MGH)

Number of Planned Subjects

Up to 25 subjects will be screened for the study with the goal of enrolling 18 for treatment. All 18 enrolled subjects will be given an opportunity to sign a consent form addendum during Weeks 18-22 to receive approximately 24 additional weeks of drug treatment.

Study Population

This study will be conducted in subjects who meet the El Escorial criteria of possible, laboratory-supported probable, probable, or definite criteria for a diagnosis of ALS. At screening, eligible subjects must be at least 18 years old and must provide written informed consent prior to screening. Subjects on a stable dose of riluzole and those not taking riluzole, and women of child-bearing age at screening are eligible for inclusion as long as they meet specific protocol requirements. Safety, tolerability, blood biomarkers, and clinical outcomes will be collected on all subjects. In a subgroup of 10 study participants (“Imaging group”) neuro-imaging will be performed. Detailed criteria are described in the body of the protocol.

Treatment Plan

RNS60 will be administered in two ways: by intravenous (IV) infusion one day a week (infusion dose: 375ml, infused over a 40-min period) and by inhalation (the remaining 6 days a week, 4 ml/day) for 24 weeks or up to approximately 48 weeks.

Duration of Treatment and Follow-up

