5 SELECTION AND WITHDRAWAL OF STUDY POPULATION

5.1 Number of Study Subjects

Approximately 25 subjects will be consented for the study. Any subject who signs consent will be considered enrolled in the study. Screening study procedures will begin after informed consent.

If a subject fails screening, at a minimum, the following information will be captured and entered in the data capture system: inclusion/exclusion criteria, demographics, screening lab results, reason for screen failure.

Fifteen (15) subjects will receive RNS60 for up to 48 weeks per study protocol and will be followed up to 52 weeks.

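### The tolerability figures in section 6.7 are computed for 15 treated subjects while most of the protocol plans 18, and they are worded as probabilities about the true rate, which the calculation does not give

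*Combined protocol and SAP*

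**What the plan says.** Section 6.7 states that the sample size rests on safety and tolerability as primary outcomes. Its tolerability statement begins "With 15 participants on active drug in this study, if 10 or more participants tolerate the drug" and continues "there is an 85% chance that the true tolerability among people with ALS is at least 75" per cent. It adds that, with 10 or more tolerating the drug, "there is only a 3% chance that the true tolerability will be as low as 40% in people with ALS". The adverse-event statement in the same section also uses 15 participants and claims over 90% chance of seeing an event of 15% incidence at least once.

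The number treated differs between sections:

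- **15:** section 6.7, and section 5.1, which says "Fifteen (15) subjects will receive RNS60 for up to 48 weeks per study protocol".
- **18:** the Protocol Summary (objectives, and planned subjects: "Up to 25 subjects will be screened for the study with the goal of enrolling 18 for treatment"), the Study Workflow, section 3.1, and section 4.1 (as an approximate number).

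Section 3.2 defines the outcome as "Tolerability, defined as the ability of subjects to complete the entire 24-week treatment portion of study", under the lead-in "For all subjects enrolled in the study, the following will be primary outcome measures". Section 5.1 says "Any subject who signs consent will be considered enrolled in the study" and expects about 25 consents; section 7.1.1 repeats that definition of enrolment.

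**The concern.** There are two main faults and one smaller one.

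1. The stated basis for the sample size is a 15-subject trial, while most of the protocol describes 18. A reader cannot tell which number the percentages are meant to support.
2. Whatever the number, section 6.7 starts from an observed count and states a probability for the true tolerability. The figures look like ordinary binomial tails, which run the other way: the chance of the count, given a true rate. A probability for the true rate needs a prior, and the plan gives none.
3. The tolerability denominator is loosely worded: subjects on active drug in 6.7, but enrolled subjects in 3.2, where 5.1 makes enrolled mean consented.

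There is no control arm, so the completer count will probably be interpreted through these sentences. As worded, they invite the reader to treat 10 completers of 15 as 85% assurance that at least three quarters of people with ALS tolerate the drug.

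**Working it through.** **Inputs.** From 6.7: n = 15, cut-off 10, true rates 75% and 40%, stated chances 85% and 3%, and an adverse-event incidence of 15%. From the Summary, Study Workflow, 3.1 and 4.1: n = 18. From 5.1: about 25 consented.

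**Step 1: reproduce the plan's figures.** The formula is P(X ≥ c | n, p) = Σ from k = c to n of C(n,k) p^k (1−p)^(n−k). With n = 15 and c = 10:

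- p = 0.75 gives 0.8516 (plan: 85%).
- p = 0.40 gives 0.0338 (plan: 3%).

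Both match. The plan's percentages are therefore chances of 10 or more completers given the true rate, at n = 15.

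**Step 2: the same quantity at n = 18.**

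| Rule | p = 0.75 | p = 0.40 |
|---|---|---|
| 10 or more of 15 (plan) | 85.2% | 3.4% |
| 12 or more of 18 (same two-thirds) | 86.1% | 2.0% |
| 11 or more of 18 | 94.3% | 5.8% |
| 10 or more of 18 (only if the count were carried over) | 98.1% | 13.5% |

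**Step 3: the statement as worded.** The probability of a true rate of at least 75%, given 10 or more of 15, is

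P(p ≥ 0.75 | X ≥ 10) = ∫ from 0.75 to 1 of P(X ≥ 10 | p) f(p) dp ÷ ∫ from 0 to 1 of P(X ≥ 10 | p) f(p) dp,

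where f is a prior. The priors below are assumptions made for illustration.

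| Prior f | P(p ≥ 0.75 given X ≥ 10) |
|---|---|
| Beta(1,1), uniform | 64.7% |
| Beta(0.5,0.5) | 78.6% |
| Beta(2,1) | 71.5% |
| Beta(2,2) | 45.7% |
| Beta(1,2) | 38.5% |

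None reaches 85%. For the second statement, P(p ≤ 0.40 | X ≥ 10) is 0.4% under the uniform prior and 0.2% to 1.3% across all five, below the stated 3%. For 12 or more of 18 under the uniform prior the two figures are 66.2% and 0.2%, so changing n does not cure the wording.

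As a separate guide to what a borderline result would show, exactly 10 of 15 is 66.7% observed, with an exact (Clopper–Pearson) 95% interval of 38% to 88%.

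**Step 4: adverse-event statement.** 1 − 0.85^15 = 0.913 and 1 − 0.85^18 = 0.946, so over 90% is true at either number. At n = 18 the incidence detected with 90% chance is 1 − 0.1^(1/18) = 0.120.

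**Step 5: denominator.** Twelve completers are 12/18 = 67% of those treated and 12/25 = 48% of those consented.

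**The case against.** The strongest reply is that little turns on this numerically. At the same two-thirds proportion, 18 subjects give 86.1% and 2.0% against 85.2% and 3.4%, and the adverse-event claim holds at both numbers. The large contrast, 98.1% and 13.5%, needs the count of 10 to be read against 18, whereas 6.7 ties it to 15. That is correct, and those figures should not drive the severity.

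The 65% depends on a prior that the plan does not supply. It illustrates the error and is not a corrected value. The reversal also cuts both ways: the 85% is too favourable under every prior tried, while the 3% is too pessimistic under every one.

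On the denominator, the enrolled wording in 3.2 mainly sets all subjects apart from the imaging group, the Summary uses enrolled to mean treated, and a screen failure never starts the treatment period. The 48% figure is therefore an unlikely reading, and this part is a tidying matter.

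One possible defence fails. Fifteen cannot be taken as 18 less dropouts, because 5.1 says 15 will receive the drug and 6.7 has 15 on active drug. By definition, a treated subject who drops out is a non-completer who stays in the denominator.

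Finally, this is an open-label pilot with no tolerability decision rule. That limits the consequences but does not make the sentences correct.

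**Conclusion.** The concern holds and should be fixed. The arithmetic in 6.7 is right for 15 subjects, but it does not describe the 18-subject trial set out in the Summary, Study Workflow, 3.1 and 4.1. The 85% and 3% are also presented as probabilities of the true rate when they are probabilities of the count.

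The mismatch in numbers moves the percentages by only about one point each at the same two-thirds proportion. The reversed wording matters more: the claimed 85% would be about 65% under a uniform prior, and between 38% and 79% under the other four tried. The reproduction of the plan's figures needs only the binomial model; the reversed reading rests on the assumed priors. No formal error rate or go/no-go decision is affected. The harm is a misleading sample-size justification and a likely over-reading of the completion result. Confidence is high.

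**What to change.** Use one treated number throughout.

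- **If 18 is intended:** change 5.1 and restate 6.7. For example: with 18 treated participants, the chance that 12 or more complete 24 weeks is 86% if the true tolerability is 75% and 2% if it is 40%. The cut-off of 12 is only an example that keeps the two-thirds proportion; the documents do not select one. Give the adverse-event figure as 94.6% at 15% incidence, or 90% at about 12%.
- **If 15 is intended:** correct the Summary, Study Workflow, 3.1 and 4.1, and keep the numbers in 6.7.
- **If 18 is 15 plus an allowance for loss:** say so, and make 5.1 and 6.7 consistent with it.

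In every case, word the percentages as the chance of reaching the count given the true tolerability. State that the denominator is all subjects who receive any RNS60, with anyone not completing 24 weeks counted as not tolerating. A rule for the number actually treated is optional.

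The cost is text only, with no added subjects or procedures. Clarifying the denominator may also touch the wording of enrolled in 3.2, 5.1 and 7.1.1. The documents do not show which number is intended or whether treatment had begun, so the restated figures should be documented before completion results are known.

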4 STUDY DESIGN

4.1 Overall Study Design and Plan

During the enrollment period, approximately 25 subjects will be screened at the Massachusetts General Hospital (MGH). Approximately 18 of these subjects are expected to be eligible to receive RNS60 per study protocol. RNS60 will be administered in two ways: by IV infusion one day a week (infusions to occur at MGH) and by inhalation (once a day for the remaining 6 days a week). All visit windows (\pm 3 days) are consecutive calendar days and are calculated from the day the participant starts study treatment (the day of the Baseline Visit).

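### Section 6.7 presents 85% and 3% as chances about the true tolerability rate given the result, but both are chances of the result at a fixed true rate

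*Combined protocol and SAP*

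**What the plan says.** Section 3.2 lists among the primary outcomes "Tolerability, defined as the ability of subjects to complete the entire 24-week treatment portion of study". Section 6.7 states that the sample size was based on safety and tolerability and works with 15 participants. It makes three probability statements on these outcomes:

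- Adverse events: with 15 participants there is "over a 90% chance of seeing at least one occurrence of any adverse event whose probability of occurrence is 15% or greater".
- Tolerability, upper reference: if 10 or more of the 15 tolerate the drug, "there is an 85% chance that the true tolerability among people with ALS is at least 75"%.
- Tolerability, lower reference: on the same result, "there is only a 3% chance that the true tolerability will be as low as 40% in people with ALS".

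Section 6.7 names no prior, Bayesian model or confidence bound, and gives no interval for the observed proportion.

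The documents disagree on the number treated. The Protocol Summary (Number of Planned Subjects) says "Up to 25 subjects will be screened for the study with the goal of enrolling 18 for treatment". Section 3.1 also gives 18, and section 4.1 says "Approximately 18 of these subjects are expected to be eligible to receive RNS60 per study protocol". Section 5.1 says "Fifteen (15) subjects will receive RNS60 for up to 48 weeks per study protocol", in line with the 15 used in 6.7.

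**The concern.** The two tolerability sentences take the result as given and state a probability about the unknown true rate. The calculation that yields 85% and 3% runs the other way: it fixes the true rate and gives the probability of the result. One cannot be exchanged for the other without a prior distribution for the true rate.

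The adverse-event sentence in the same paragraph conditions correctly, because it fixes the event probability at 15% and gives the chance of seeing at least one event. The PET power sentence likewise conditions on the true difference. This points to a drafting slip in the tolerability sentences, not a deliberate Bayesian statement.

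What is at stake is how a primary outcome is read. A reader who sees 10 or 11 of 15 complete could cite 6.7 as 85% assurance that true tolerability is 75% or more, although 10/15 is an observed rate of 67%, itself below 75%.

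**Working it through.** **Inputs.** From 6.7: n = 15, cut X ≥ 10, reference rates 75% and 40%, stated figures 85% and 3%. From the Protocol Summary and sections 3.1 and 4.1: the alternative n = 18. The priors below are assumptions, since the plan gives none.

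**1. Reproduce the printed figures.** With X ~ Binomial(15, p), P(X ≥ 10 | p) = Σ C(15,k) p^k (1−p)^(15−k), summed over k = 10 to 15.

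- p = 0.75: 0.8516, printed as 85%.
- p = 0.40: 0.0338, printed as 3%.

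A strict cut (X > 10) gives 0.686 and 0.009 and does not match. The printed numbers are therefore probabilities of the result at a fixed true rate. The adverse-event figure also reproduces: 1 − 0.85^15 = 0.913.

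**2. How often the result occurs below 75% (no prior needed).**

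| True rate | P(X ≥ 10 of 15) |
|---|---|
| 70% | 0.722 |
| 65% | 0.564 |
| 60% | 0.403 |

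The result separates 75% from these lower rates only weakly.

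**3. What the sentences literally claim.** For a prior density π(p), P(p ≥ 0.75 | X ≥ 10) = ∫ from 0.75 to 1 of P(X ≥ 10 | p)π(p)dp, divided by the same integral from 0 to 1. For exactly x completers the posterior under a Beta(a, b) prior is Beta(a + x, b + 15 − x).

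| Assumed prior | Prior P(p ≥ 75%) | Given X ≥ 10 | Given X = 10 |
|---|---|---|---|
| Flat, Beta(1,1) | 25% | 65% | 19% |
| Jeffreys, Beta(0.5,0.5) | 33% | 79% | 22% |
| Beta(7.5,2.5) | 55% | 69% | 31% |
| Beta(3,1) | 58% | 77% | 28% |
| Beta(5,1) | 76% | 86% | 38% |
| Beta(9,1) | 92% | 95% | 58% |

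For the event as written (10 or more), the answer runs from 65% to 95% depending on the prior. At exactly 10/15 none of the six priors comes near 85%.

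**4. The 40% sentence.** Under the flat and Jeffreys priors, P(p ≤ 0.40) is 0.4% and 0.3% given X ≥ 10, and 1.9% and 1.8% at exactly 10/15. The other priors give smaller values. The printed 3% does not overstate assurance.

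**5. Interval at the cut.** The Clopper-Pearson 95% interval for 10/15 is 38.4% to 88.2%.

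**6. If n is 18.**

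| Cut | P(result \| 75%) | P(result \| 40%) |
|---|---|---|
| 10 of 18 | 0.981 | 0.135 |
| 12 of 18 | 0.861 | 0.020 |

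The printed 85% and 3% with a cut of 10 hold only for n = 15. The Clopper-Pearson 95% interval for 12/18 is 41.0% to 86.7%.

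**The case against.** The best case for leaving the text alone is that the numbers are correct operating characteristics, the sample size does not change, and nothing in the trial turns on the cut. Section 5.3.2 lists grounds for termination without a tolerability threshold, and section 10.1 leaves safety stopping to the investigators' review of adverse events. This is a single-centre, open-label pilot. That stands, and it limits the harm to interpretation.

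Second, calling the 75% sentence optimistic depends on the prior. With Beta(5,1), which already puts 76% on a true rate of at least 75%, the probability given 10 or more is 86%, close to the printed figure; with Beta(9,1) it is higher still. This also stands: for the event as written, the direction of the error is not fixed. It does not rescue the sentence, because the plan states no such prior and the printed 85% was not obtained from one. Nor does it affect a borderline result: at exactly 10/15 those two favourable priors give 38% and 58%.

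Third, the 40% sentence does no practical harm. Agreed; it has the same reversal but is not optimistic.

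Finally, the conflict between 15 and 18 is a separate inconsistency and no evidence of the reversal. It matters here only because the corrected sentences need a definite n. The cut of 12 of 18 used above is not in the documents; it keeps the 67% proportion, and the choice of cut belongs to the sponsor.

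**Conclusion.** The concern holds. Both tolerability sentences in 6.7 reverse the conditioning, and neither follows from the calculation behind it. The arithmetic and the sample size are unaffected.

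Only the 75% sentence is likely to mislead, and mainly at or just above the cut. At exactly 10/15, support for a true rate of 75% or more is 19% to 22% under the flat and Jeffreys priors and at most 58% under the most favourable prior tried, against a printed 85%. For 10 or more as a whole the gap is smaller (65% to 79% under flat and Jeffreys) and closes under strongly favourable priors. The findings that rest on no prior are the reversal itself, the 72%, 56% and 40% chances of the result at true rates of 70%, 65% and 60%, and the 38% to 88% interval at 10/15.

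The text should be corrected because it misstates a property of a primary outcome on which the sample size was based. It does not threaten the conduct of the trial.

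**What to change.** First settle the number treated, so that 6.7 agrees with the Protocol Summary and sections 3.1, 4.1 and 5.1. Then replace the two tolerability sentences.

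- If n is 15: *If true tolerability is 75%, the probability that 10 or more of 15 participants complete is 85%; if it is 40%, the probability is 3%.*
- If n is 18 and the sponsor keeps the 67% proportion: *If true tolerability is 75%, the probability that 12 or more of 18 participants complete is 86%; if it is 40%, the probability is 2%.* With another cut, recompute both figures. A cut of 10 carried over to 18 gives 98% and 13%.

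In either case add: *Tolerability will be reported as the observed proportion with an exact (Clopper-Pearson) 95% confidence interval. A result at the cut-off (67%) does not by itself support a claim that true tolerability is at least 75%.* Another accepted interval would serve if it is named in advance.

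The cost is two reworded sentences and a short reporting statement in 6.7. At n = 15 the figures 85% and 3% stay and only their meaning changes, so the plan no longer claims 85% assurance of a true rate of at least 75%. Data, endpoints and conduct do not change.
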